1.2 SPECIFIC AIMS

Hypothesis: The initiation of LTLR-WB resuscitation in the prehospital setting with continuation through the in-hospital acute resuscitation phase of care will significantly reduce the morbidity and mortality attributable to hemorrhagic shock post-injury as compared to standard prehospital and in-hospital resuscitation practice.

Specific Aims:

Specific Aim I: Determine the feasibility and most appropriate study population that will lead to a large multicenter clinical trial designed to evaluate the effectiveness of prehospital through inhospital LTLR-WB as compared to standard care practice in patients at risk of hemorrhagic shock.

Specific Aim II: Determine if prehospital through in-hospital LTLR-WB reduces 28-day mortality, in-hospital mortality, multiple organ dysfunction, presenting coagulopathy, 24-hour resuscitation requirements and early mortality as compared to standard of care prehospital and in-hospital resuscitation in patients at risk of hemorrhagic shock.

Specific Aim III: Determine the primary drivers by which prehospital through in-hospital LTLR-WB improves clinical, resuscitative and hemostatic outcomes as compared to standard of care prehospital and in-hospital resuscitation in patients at risk of hemorrhagic shock.

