Multiple Organ Failure (MOF): Organ dysfunction will be evaluated via the Denver Post-injury Multiple Organ Failure Score, a well-validated scoring system in injured patients and characterized as an incidence rate (%) and as MOF free days.^{84,87} Patients who are never admitted to the ICU or those with a length of ICU stay of less than 48 hrs will be considered to have a Denver score of 0. A summary of the Denver score may be calculated by summing the worst scores of each of the individual systems over the course of the ICU stay. A summary Denver score > 3 will be classified as MOF. Scores will be determined daily up until ICU discharge.⁸⁷ Mean Denver Post-injury MOF Score: As the primary endpoint for the pilot trial, the 3 highest (worst) daily Denver scores will be averaged and compared across the treatment arms. Patient not in the ICU will be given a score of 0. Acute Respiratory Distress Syndrome (ARDS): The Berlin definition for mild ARDS (PaO_2/FIO_2 , ≤ 300 mm Hg + timing, imaging and origin criteria) will be utilized as a threshold value to determine the incidence of ARDS and will be further stratified into Moderate (PaO_2/FIO_2 , ≤ 200) and Severe (PaO_2/FIO_2 , \leq 100).⁸⁶(Nosocomial Infection (NI): The CDC criteria for the diagnosis of hospital acquired pneumonia and blood stream infection will be utilized (www.cdc.gov/nhsn) Mortality: We will derive the time to a mortality event from the time of admission for 6 hour and 24 hour mortality rates over the initial 24 hours. All cause in-hospital and 28-day mortality will be similarly determined from the date of admission. 7) Blood component transfusion and resuscitation requirements at 24 hours: Blood component transfusion needs per unit (PRBC, FFP, PLT) will be recorded over the first 24 hours of admission with 6-hour incremental totals. For every unit of LTLR-WB that is transfused each will be designated as 1 unit of PRBC, 1u of FFP and a single pack of platelets. Similar recording of crystalloid volume and colloid volume of the initial 24 hours following admission will be undertaken. 8) Acute Hemolytic Transfusion Reactions: We will compare the incidence AHTRs (CDC NHSN Hemovigilance Surveillance definition) and will measure arrival serum haptoglobin levels. 9) Length of hospital and intensive care unit (ICU) stay: Length of stay will be determined from the date of admission for all enrolled patients.

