Mechanistic Outcomes: The principle factors that may be responsible for beneficial clinical outcome effects associated with or attributable to LTLR-WB resuscitation when initiated early in the prehospital phase of injury are an important and essential objective of the proposed pilot trial. We will compare across treatment arms: 1) Coagulopathy: Coagulopathy will be assessed via PT/PTT/INR and rapid Thromboelastography (r-TEG) measurements. 2) Platelet Function: We will assess platelet activation, aggregation, and adhesion via flow cytometry analysis, whole blood aggregometry measurements and flow chamber analysis under shear stress conditions, respectively in a subset of patients.^{88,89} 3) Glycocalyx integrity: We will assess glycocalyx integrity by measuring serum concentrations of Syndecan-1 and Hyaluronan by ELISA at inhospital time points. 3) Donor Exposure, Age and Volume of Transfusion Products: During the prehospital and in-hospital acute resuscitation phase of the study the number donors from all transfused products blood products, the age of all LTLR-WB and PRBCs from the standard of care arm and overall transfusion volumes will be recorded and compared.

Blood Sampling and In-Hospital Measurements: In-hospital phase blood sampling will occur upon arrival (+ 4 hrs) and at 12 hours (+/- 12hrs) and 24 hours (+/- 12hrs) from time of arrival. Timing of samples will need to be flexible based upon patient availability and logistic factors. This early in-hospital sampling will allow adequate assessment of the benefits of early LTLR-WB resuscitation and appropriate characterization of the proposed clinical and mechanistic outcomes. TEG analysis at arrival, 12hr and 24hr time points will be performed on a TEG[®] 5000 Thromboelastograph[®] Hemostasis Analyzer.

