2.9 STATISTICAL ANALYSIS

The overarching goals for the pilot trial are to evaluate safety, efficacy and feasibility of a LTLR-WB prehospital through in-hospital protocol to plan for the successful execution of a large, multicenter clinical trial. All analyses will be performed based on the intent-to-treat principle for the prehospital randomization and analyses will include all enrolled patients grouped by randomization assignment. This pilot study will guide the calculation needed for the large, multicenter clinical trial and will provide estimation for intra-cluster correlation coefficient and sample size variation across clusters. We will report 95% confidence intervals for all measurements

Safety and Efficacy Analysis: 28-day mortality is the primary safety and efficacy outcome and will be compared across randomized groups. Utilizing intention to treat principles we will compare the LTLR-WB and Standard of Care arms using a pooled Z test for comparing two independent proportions. We will additionally perform survival analysis for all mortality outcomes including 3hr, 6hr, 24hr, and 28day time points across the two arms of the study testing the differences using log rank test.

Eligibility, Enrollment, and Subject Accrual Anlaysis: The feasibility of enrollment will be evaluated by determining 1) the number of patients that meet the eligibility criteria for the trial; 2) the proportion of eligible patients that can be randomized and 3) the proportion of eligible patients who are enrolled in the trial. These proportions will be estimated directly as the observed ratio of numbers of patients, and 95% confidence intervals will be calculated to understand the likely range of values for a larger study with a comparable research protocol. The reasons why patients are not enrolled including frequencies of individual exclusions and the proportion of patients declining participation or not able to be randomized will be described. Rate of subjects' accrual per month with 95% C.I. will be calculated.

Adherence and Minimization of Bias: Adherence rates for each treatment arm of the protocol will be ascertained as the proportion of enrolled patients who adhere to the intervention (LTLR-WB vs. standard care) as assigned. Estimated proportions and 95% confidence intervals will be created. The trial has been designed to negate intervention arm crossover and maximize follow-up completion.

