Sample Size Justification for Pilot Trial: Assuming a baseline in-hospital mortality risk of 33% in the control arm as was demonstrated in the recently completed PAMPer trial with all cause in-hospital mortality as the primary outcome, enrolling **56 patients in each arm, 112 total patients** and using a 2 sided alpha of 0.05, the study will have a 80% power to detect a 22% (33% to 11%) or greater difference in in-hospital mortality. Based upon current PAMPer clinical outcome data and the additional benefit attributable to LTLR-WB when it is initiated in the prehospital setting, the current proposed mortality difference is clinically meaningful and of sufficient magnitude to influence clinical practice for a pilot trial. The above sample size will provide more than sufficient power for the originally planned feasibility outcomes as we have increased our sample size by 24%. The above power analysis was generated assuming 2 sequential tests using the O'Brien-Fleming spending function to determine test boundaries which are depicted in the following table and graph.

Details	Details when Spending = O'Brien-Fleming, N1 = 56, N2 =56, P1 = 0.1100, P2 = 0.3300							
		Lower	Upper	Nominal	Inc	Total	Inc	Total
Look	Time	Bndry	Bndry	Alpha	Alpha	Alpha	Power	Power
1	0.50	-2.96259	2.96259	0.003051	0.003051	0.003051	0.164669	0.164669
2	1.00	-1.96857	1.96857	0.049002	0.046949	0.050000	0.636252	0.800921
Drift 2.	81024							

Based upon the busy air medical service at the University of Pittsburgh, the bases to be utilized for the pilot trial, 61 patients who met all inclusion and exclusion criteria for the current proposed pilot trial, were admitted to Presbyterian Hospital, consented and were enrolled (www.pamperstudy.com) over a 12 month period 6/2015-5/2016. Based upon a planned enrollment period of 2.5 years, this sample size is feasible after accounting for consent rates and exclusions.

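### 24-hour product totals and the later mechanistic markers are compared by arm with no allowance for death inside the measurement window

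*Combined protocol and SAP*

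**What the plan says.** Section 2.8 (Mechanistic Outcomes) lists PT/PTT/INR and rapid TEG, platelet function in a subset of patients, and Syndecan-1 and Hyaluronan, all to be compared between arms. The sampling rule begins "In-hospital phase blood sampling will occur upon arrival (+ 4 hrs) and at 12 hours (+/- 12hrs) and 24 hours (+/- 12hrs", counted from arrival, with timing left flexible for patient availability. Read literally, the windows are 0 to 4 h for the arrival sample, 0 to 24 h for the 12 h sample and 12 to 36 h for the 24 h sample.

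Section 2.8 (Clinical Outcome Definitions) says product units "will be recorded over the first 24 hours of admission with 6-hour incremental totals". Crystalloid and colloid are recorded over the same period.

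Section 2.9 applies intention to treat, so that "analyses will include all enrolled patients grouped by randomization assignment", and reports absolute and relative differences by arm with 95% confidence intervals.

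In section 1.2, Aim II names both 24-hour resuscitation requirements and early mortality. Aim III reads, in part, "Determine the primary drivers by which prehospital through in-hospital LTLR-WB improves clinical, resuscitative and hemostatic outcomes".

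No section gives a rule for a patient who dies before a sample is due or before 24 hours have passed. The only value-assignment rule of this kind is for the Denver score, which is set to 0 without an ICU stay or with one under 48 hours. Appendix 8 has no rows for the mechanistic markers. Its Table 4 does show 6 h, 24 h and 28-day mortality by arm, in the same table as the 24-hour blood components.

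**The concern.** A patient who has died cannot give a later sample, and that patient's product total stops growing at death. If the arms differ in early deaths, which Aim II hopes to show, the later marker comparison is between two differently selected groups of survivors. Standard care would have lost more of its sickest patients, so its remaining markers would look better than the arm as a whole. Its 24-hour totals would also include more short, truncated records and so look lower.

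Both effects make whole blood look worse than it is. A reader of the pilot could conclude that there is no hemostatic or glycocalyx effect at 24 h, or that whole blood raises product use, when more patients simply lived to be sampled and transfused. The pilot is meant to inform a large multicenter trial, and selection by death does not shrink as the sample grows.

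**Working it through.** **Step 1. The plan's own figure.** Section 2.9 gives the inputs: "Assuming a baseline in-hospital mortality risk of 33% in the control arm"; "56 patients in each arm, 112 total patients"; "using a 2 sided alpha of 0.05, the study will have a 80% power to detect a 22% (33% to 11%) or greater difference"; and "assuming 2 sequential tests using the O'Brien-Fleming spending function", with bounds ±2.96259 and ±1.96857. The mean proportion is (0.33 + 0.11)/2 = 0.22. The drift is 0.22/√(2 × 0.22 × 0.78/56) = 2.81024, as printed. Two-look power from the bivariate normal (correlation √0.5) is 0.8010, against the printed 0.800921. The plan's figure reproduces. It is the only design calculation; none is given for markers or totals.

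**Step 2. Deaths inside the window.** The share f of in-hospital deaths that fall within 24 h is an assumption. At 33% v 11%, the proportion dead by 24 h is f times each rate, multiplied by 56 for counts (standard care v whole blood):

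| f | Dead by 24 h | Deaths per 56 | Alive at 24 h | Marker SE, √(1/n₁ + 1/n₂) |
|---|---|---|---|---|
| 30% | 9.9% v 3.3% | 5.5 v 1.8 | 50.5 v 54.2 | 0.20 SD |
| 50% | 16.5% v 5.5% | 9.2 v 3.1 | 46.8 v 52.9 | 0.20 SD |
| 70% | 23.1% v 7.7% | 12.9 v 4.3 | 43.1 v 51.7 | 0.21 SD |

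**Step 3. Markers, with no true effect.**

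- *Extreme bound.* If the dead would have held exactly the worst values, the survivor mean shifts by −φ(z)/(1−d), where d is the share dead and z = Φ⁻¹(1−d). For f = 1/2 this is −0.297 SD (d = 0.165) and −0.118 SD (d = 0.055), an arm difference of 0.18 SD against whole blood. For f = 1/3 and 2/3 the difference is 0.13 and 0.23 SD.
- *Correlation 0.5 between marker and death.* Half of these: 0.06 to 0.11 SD.
- *Simulation, 1,000,000 patients per arm.* Severity–death correlation 0.6, marker–severity correlation 0.3 to 0.7, f from 30% to 70%: 0.02 to 0.10 SD against whole blood. The central case (f = 50%, marker correlation 0.5) gave 0.054, which agrees with 0.18 × 0.6 × 0.5 = 0.054.

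**Step 4. The 24-hour total, with no true effect on need.**

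- *Simple formula.* If a dying patient receives k times a survivor's total, the arm difference (whole blood minus standard care) shifts by (0.11 − 0.33) × f × (k − 1) of the survivor mean. For k = 0.5 this is +3.7% at f = 1/3 and +7.3% at f = 2/3.
- *Simulation.* Would-be total lognormal with median 8 units, rising with severity (log-scale SD 0.7), mean 8 × exp(0.7²/2) = 10.2 units. Section 2.3 puts over 79% of 24-hour product in the first 4 hours; 79% was used, spread evenly, with the other 21% spread over hours 4 to 24. Severity–death correlation was 0.6, median time to death 1, 3 or 6 h, and f 30% to 70%. Observed means were 0.4 to 1.6 units higher on whole blood (+4% to +22%). The top value needs f = 70% and a median death time of 1 h (9.03 v 7.40 units).
- *Survivors only.* The difference remains +0.6 to +1.0 units, so dropping the dead does not remove it.

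**Step 5. Which time points.** The 24 h sample cannot be taken before 12 h, so every earlier death is excluded from it. The 12 h window opens at arrival, so some early deaths can still contribute. Arrival samples are little affected.

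**The case against.** The strongest reply is that this is a pilot whose secondary differences are estimated for safety and planning, that the plan nowhere says it will analyse survivors only, and that early deaths are already on view. Section 2.8 plans mortality comparisons at 3, 6 and 24 h, and Appendix 8 Table 4 shows 6 h and 24 h mortality by arm in the same table as the totals. All of this stands, and it limits the point. It does not remove it: mortality elsewhere in a table does not tell a reader how many patients lie behind each marker mean or each 6-hour increment.

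Several stronger readings are tempting and are not supported.

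- *That the marker bias is about a third of the detectable difference.* With 47 v 53 patients that difference is 2.80 × 0.20 = 0.56 SD, and 0.18/0.56 is about a third. But 0.18 SD needs the dead to hold exactly the worst values. Nor is being dead by 24 h the same as being unsampled, given the wide windows. Platelet function, measured only in a subset, has a different denominator again.
- *That truncation could push the totals either way.* With k = 2 the formula gives −7% to −15%. That describes dying patients who used more product; preventing those deaths would truly lower use, which is not truncation.
- *That the totals breach the all-enrolled principle.* Every enrolled patient has an observed 24-hour total. The difficulty is how to interpret it.
- *That the arrival sample should therefore become the main mechanistic comparison.* Arrival reflects mainly the prehospital phase, whereas Aim III covers prehospital through in-hospital treatment.
- *That ranking deaths worst on a marker would show mechanism.* Such a comparison would favour whole blood through survival alone, even with no marker effect.

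**Conclusion.** The point holds in a limited form. Totals truncated at death and survivor-only later markers are compared by arm without allowance for early death, and if whole blood reduces early deaths both would tend to run against it. They could mask a benefit or suggest extra product use.

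For markers the likely shift is 0.02 to 0.11 SD, at most about half of the 0.2 SD standard error; 0.13 to 0.23 SD arises only in the extreme case. For the 24-hour total it is about +4% to +7% when dying patients receive half a survivor's product, and up to about +22% under the simulation's harshest settings. All these sizes rest on the planned 33% v 11% mortality and on assumed death timing, correlations and product use that the documents do not give. A benefit that arose only after the sampling windows had closed would produce no distortion.

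The 24 h sample is most affected and the 12 h sample less so. Arrival measures are little affected, and the primary mortality comparison not at all. This merits a change to the analysis text and tables; it does not call the design into question.

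**What to change.** In section 2.9 and Appendix 8 Table 4:

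1. **Totals.** Report the 6-hour product increments by arm, with the number alive at the start of each interval. Add one supporting rank-based comparison of the 24-hour total in which deaths before 24 h are ranked worst.
2. **Markers.** Describe 12 h and 24 h results as *among patients alive and sampled*. Beside each, give by arm the number dead before sampling and the number alive but not sampled. State that a null or adverse later difference will not be read as absence of effect without those counts.

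The cost is a few sentences and table rows. The increments and times of death are already to be recorded, and no new visits, samples or changes to care are needed. The downside is that the death-ranked comparison mixes survival with product use, so it should remain supporting only.

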2.9 STATISTICAL ANALYSIS

The overarching goals for the pilot trial are to evaluate safety, efficacy and feasibility of a LTLR-WB prehospital through in-hospital protocol to plan for the successful execution of a large, multicenter clinical trial. All analyses will be performed based on the intent-to-treat principle for the prehospital randomization and analyses will include all enrolled patients grouped by randomization assignment. This pilot study will guide the calculation needed for the large, multicenter clinical trial and will provide estimation for intra-cluster correlation coefficient and sample size variation across clusters. We will report 95% confidence intervals for all measurements

Safety and Efficacy Analysis: 28-day mortality is the primary safety and efficacy outcome and will be compared across randomized groups. Utilizing intention to treat principles we will compare the LTLR-WB and Standard of Care arms using a pooled Z test for comparing two independent proportions. We will additionally perform survival analysis for all mortality outcomes including 3hr, 6hr, 24hr, and 28day time points across the two arms of the study testing the differences using log rank test.

Eligibility, Enrollment, and Subject Accrual Anlaysis: The feasibility of enrollment will be evaluated by determining 1) the number of patients that meet the eligibility criteria for the trial; 2) the proportion of eligible patients that can be randomized and 3) the proportion of eligible patients who are enrolled in the trial. These proportions will be estimated directly as the observed ratio of numbers of patients, and 95% confidence intervals will be calculated to understand the likely range of values for a larger study with a comparable research protocol. The reasons why patients are not enrolled including frequencies of individual exclusions and the proportion of patients declining participation or not able to be randomized will be described. Rate of subjects' accrual per month with 95% C.I. will be calculated.

Adherence and Minimization of Bias: Adherence rates for each treatment arm of the protocol will be ascertained as the proportion of enrolled patients who adhere to the intervention (LTLR-WB vs. standard care) as assigned. Estimated proportions and 95% confidence intervals will be created. The trial has been designed to negate intervention arm crossover and maximize follow-up completion.

Estimates for Trial Secondary Clinical Outcomes: We will estimate the mean differences in the average Denver post-injury MOF score derived from the 3 highest daily scores between two treatment groups as the main clinical outcome for the pilot trial. We will also record and compare the overall proportion of patients who developed MOF based on Denver score > 3 and compare MOF free days. Similarly, the incidence of ARDS, NI, mortality (6hr, 24hr and 28 day) and hemolytic transfusion reactions will be recorded. We will perform survival analysis for all mortality outcomes. Blood component and resuscitation volumes over the initial 24 hours, length of ICU stay, days on a ventilator, and total hospital stay will be also be determined. Estimated proportions and means and 95% confidence intervals will be created for each outcome using the data from the entire pilot trial (i.e. combining the data from the two assigned treatment arms). Absolute and relative differences for continuous levels and event rates by assigned treatment will be estimated and 95% confidence intervals will be calculated to identify potential treatment differences for safety and for study planning purposes. Subgroup analyses will be exploratory and be based on baseline factors specified prior to the initiation of the trial.

The Following Outcomes Will Be Recorded:

- 1. The average Denver post-injury MOF score derived from the 3 highest daily scores. Differences between these averages will be estimated across the study two arms.
- Proportion of patients who developed MOF based on Denver score > 3 and compare MOF free days across the study two arms.
- 3. The incidence of ARDS, NI, mortality (6hr, 24hr and 28 day) and hemolytic transfusion reactions will be recorded and compared across the study two arms
- 4. Survival analysis in relation to all causes of death.
- 5. Blood component and resuscitation volumes over the initial 24 hours,
- 6. Length of ICU stay, days on a ventilator, and total hospital stay will be also be determined.

Statistical Distributions of Enrolled Sample of Patients: Descriptive statistics, including means, standard deviations, medians, interquartile ranges, minimums, maximums, and frequency distributions, will be examined for all relevant measures. Transformations of measures will be considered based on distribution diagnostics and outlier analyses. The baseline characteristics of the patients in the entire trial will be described and 95% confidence intervals will be calculated to identify potential differences in baseline characteristics.

- 1. Estimated proportions and means and 95% confidence intervals will be created for each outcome using the data from the entire pilot trial (i.e. combining the data from the two assigned treatment arms).
- 2. Absolute and relative differences for continuous levels and event rates by assigned treatment will be estimated and 95% confidence intervals will be calculated to identify potential treatment differences for safety and for study planning purposes. Subgroup analyses will be exploratory and be based on baseline factors specified prior to the initiation of the trial.
- **3.** Descriptive statistics, including means, standard deviations, medians, interquartile ranges, minimums, maximums, and frequency distributions, will be examined for all relevant measures.

- Transformations of measures will be considered based on distribution diagnostics and outlier analyses.
- The baseline characteristics of the patients in the entire trial will be described and 95% confidence intervals will be calculated to identify potential differences in baseline characteristics.

Sample Size Justification for Pilot Trial: Assuming a baseline in-hospital mortality risk of 33% in the control arm as was demonstrated in the recently completed PAMPer trial with all cause in-hospital mortality as the primary outcome, enrolling **56 patients in each arm, 112 total patients** and using a 2 sided alpha of 0.05, the study will have a 80% power to detect a 22% (33% to 11%) or greater difference in in-hospital mortality. Based upon current PAMPer clinical outcome data and the additional benefit attributable to LTLR-WB when it is initiated in the prehospital setting, the current proposed mortality difference is clinically meaningful and of sufficient magnitude to influence clinical practice for a pilot trial. The above sample size will provide more than sufficient power for the originally planned feasibility outcomes as we have increased our sample size by 24%. The above power analysis was generated assuming 2 sequential tests using the O'Brien-Fleming spending function to determine test boundaries which are depicted in the following table and graph.

Details	Details when Spending = O'Brien-Fleming, N1 = 56, N2 =56, P1 = 0.1100, P2 = 0.3300							
		Lower	Upper	Nominal	Inc	Total	Inc	Total
Look	Time	Bndry	Bndry	Alpha	Alpha	Alpha	Power	Power
1	0.50	-2.96259	2.96259	0.003051	0.003051	0.003051	0.164669	0.164669
2	1.00	-1.96857	1.96857	0.049002	0.046949	0.050000	0.636252	0.800921
Drift 2.	81024							

Based upon the busy air medical service at the University of Pittsburgh, the bases to be utilized for the pilot trial, 61 patients who met all inclusion and exclusion criteria for the current proposed pilot trial, were admitted to Presbyterian Hospital, consented and were enrolled (www.pamperstudy.com) over a 12 month period 6/2015-5/2016. Based upon a planned enrollment period of 2.5 years, this sample size is feasible after accounting for consent rates and exclusions.

